#### **6.1.7.6 Creatinine Clearance**

If calculated creatinine clearance (by Schwartz formula for children aged 3 to < 12 years and Crockcroft-Gault formula for children  $\geq$  12 years) is confirmed to have decreased to < 50 mL/minute, medical evaluation should include a full review of current medications, including those taken on an as needed basis, those which are sold over the counter and any dietary and herbal supplements, and appropriate dose reduction or discontinuation based on impaired renal function should be done (if applicable). Ribavirin dose should be adjusted according to local RBV prescribing information/product label or per the discretion of the investigator. Alternative management of RBV dose in the setting of reduced renal function will require approval of the AbbVie Therapeutic Area Medical Director.

Schwartz formula (children 3 to < 12 years old):

$$\text{GFR Estimate} = \frac{[\text{Height (cm)} \times 0.55]}{[\text{Serum creatinine } (\mu\text{mol/L}) \times 0.01131]}$$

Crockcroft-Gault formula (Children  $\geq$  12 years old):

$$\text{CrCl} = \frac{[(140 - \text{Age}) \times \text{Mass (in kg)} \times (0.85 \text{ if female})]}{[72 \times \text{Serum creatinine (in mg/dL)}]}$$

The investigator should also consider whether drug-drug interactions with concomitant medications may have contributed to the decrease in creatinine clearance, and whether discontinuation or substitution of the possible interacting drug might be needed. For example, drug interactions between DAAs and some antihypertensive medications could

potentially increase exposures of the antihypertensive, which may lead to reduction in renal function. If anti-hypertensive medications are adjusted, vital signs should be monitored to ensure appropriate blood pressure control. Refer to Section 5.2.3 for additional information regarding drug-drug interactions.

If creatinine clearance improves, the site should perform all necessary readjustment of any dose modifications that have been made. If creatinine clearance improves to above the level that triggered the RBV dose reduction, RBV dose may be increased accordingly.

The Investigator should ensure that any concomitant medication changes, RBV dose reductions, and study drug discontinuations, as well as consequent related adverse events are entered into the appropriate eCRFs.

## 8.0 Statistical Methods and Determination of Sample Size

### 8.1 Statistical and Analytical Plans

The pharmacokinetic analysis will be performed separately for Part 1 and Part 2. For population pharmacokinetic analyses, data from Part 1 and Part 2 will be combined if needed. The efficacy, resistance, growth and development and safety analyses will be performed across Parts 1 and 2 combined. Analyses on durability of response, resistance, growth and development outcome, patient-reported outcome, and clinical outcomes will be performed through Post-Treatment Week 24 in Parts 1 and 2 and after Post-Treatment Week 24 for all subjects who enter Part 3.

An interim analysis will occur once all subjects complete PT Week 12 or prematurely discontinue from the study. Final analysis will occur after the completion of the whole study.

SAS® (SAS Institute, Inc., Cary, NC) for the UNIX operating system will be used for all analyses. All statistical tests and all confidence intervals will be two-sided with an  $\alpha$  level of 0.05.

The intention-to-treat populations, ITT will consist of all subjects who receive at least one dose of study drug in Part 1 or Part 2 of the study. The intention-to-treat population for Part 3, ITT-3, will consist of all subjects who enter Part 3.

Efficacy endpoints and growth and development outcomes will be summarized across Parts 1 and 2 for the ITT population. Growth outcomes including standardized height, waist circumference, Tanner pubertal stage, and growth rate as defined in protocol Section 5.3.1.1 will be summarized through Post-Treatment Week 24 in Parts 1 and 2 and through the end of Long-term Follow-up in Part 3, for ITT-3.

No data will be imputed for any efficacy or safety analyses except for analyses of the SVR endpoints. For EQ-5D-3L health state index, no imputation will be performed for missing items.

HCV RNA values will be selected for the SVR12 and SVR24 analyses based on defined visit windows. When there is no HCV RNA value in a visit window based on defined visit windows, the closest values before and after the window, regardless of the value chosen for the subsequent and preceding window, will be used for the flanking imputation described below.

If a subject has a missing HCV RNA value at a post-baseline visit but with undetectable or unquantifiable HCV RNA levels at both the preceding value and succeeding value, the HCV RNA level will be considered undetectable or unquantifiable, respectively, at this visit for this subject. For SVR12 and SVR24 analysis, if there is no value in the appropriate window but there is an HCV RNA value after the window, then it will be imputed into the SVR12 or SVR24 window, respectively. Subsequent to this flanking imputation, if a subject is missing a value for the visit window associated with the analysis, the subject will be imputed as a visit failure (i.e., not undetectable or unquantifiable).

The 95% confidence interval for any simple percentage (e.g., SVR12, SVR24, and percentage of subjects with ALT normalization) will be calculated using normal approximation to the binomial distribution if the percentage is not 0% or 100%; otherwise, Wilson's score method will be used.

Detailed statistical methods for all endpoints will be provided in the Statistical Analysis Plan (SAP).

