**Statistical Methods (Continued):**

**Efficacy (Continued):**

The main secondary endpoints are:

1. The percentage of subjects who achieve SVR12 summarized by formulation, age and weight group and across all subjects.
2. The percentage of subjects who achieve SVR24 by formulation, age and weight group, across all the subjects, and across all subjects on the adult formulations;
3. The percentage of subjects with ALT normalization during treatment, defined as ALT ≤ ULN at the final treatment visit for subjects with ALT > ULN at baseline, by formulation, age and weight group, across all subjects, and across all subjects on the adult formulations.

For the secondary efficacy endpoints, the simple percentage will be calculated along with the 2-sided 95% confidence interval. For both primary and secondary endpoints, the normal approximation to the binomial distribution will be used if the rate is not 0% or 100%, otherwise the Wilson's score method will be used to calculate the confidence interval. The lower bound of the 2-sided 95% confidence interval of the SVR24 rate across all subjects in the study will also be compared to 67%.

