### **3.2 Benefits and Risks**

Part 1 of this study is a Phase 2 study in which eligible HCV GT1-infected pediatric subjects will receive OBV, PTV, RTV and DSV with or without RBV for 12 weeks. Part 2 of this study is a Phase 3 study in which eligible genotype 1 or 4-infected subjects will receive OBV/PTV/RTV with or without DSV and with or without RBV for 12 or 24 weeks depending on HCV genotype, sub-genotype and cirrhosis status. OBV/PTV/RTV and DSV with or without RBV was evaluated in > 2300 adult subjects with HCV GT1 infection in six Phase 3 studies. OBV/PTV/RTV and DSV with or without RBV achieved SVR12 greater than 97% overall in HCV GT1-infected subjects, including those with compensated cirrhosis, with the label recommended regimens. OBV/PTV/RTV with or without RBV was evaluated in 135 adult subjects with HCV GT4 infection in a Phase 2 study. Similarly high SVR12 rates (100%) were observed in this study with OBV/PTV/RTV with RBV.

OBV/PTV/RTV and DSV with or without RBV was well tolerated in the Phase 3 studies in genotype 1-infected adults with discontinuation due to AEs approximately 1%. Adverse events that are known and those not previously described, may occur as detailed in the informed consent and assent for this study. In addition, subjects may experience inconvenience or discomfort related to the study visits or study procedures.

Post-marketing cases of hepatic decompensation were reported in patients treated with OBV/PTV/RTV with or without DSV with or without RBV, some of which resulted in fatalities or necessitated liver transplants. These occurrences were observed in patients who already had highly advanced or decompensated cirrhosis prior to starting treatment. In this study, patients with a history of or existing decompensation will not be included in the study. Other risks associated with OBV/PTV/RTV with or without DSV and with or

without RBV include the risks of toxicity and virologic failure. Adverse events associated with treatment have been limited and manageable based on the results from the Phase 2/3 studies. Given the potential high rate of cure in HCV GT1 and GT4-infected subjects, the risk-benefit profile is favorable.

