In Part 1, the primary objectives are to assess the pharmacokinetics, efficacy and safety of OBV, PTV, RTV and DSV with or without RBV in HCV GT1-infected, treatment-naïve pediatric subjects. Part 1 will include approximately 36 subjects. At least 12 subjects will enroll in each of the 3 age year groups,  $\geq 3$  to 8,  $\geq 9$  to 11, and  $\geq 12$  to 17. Enrollment will begin with pediatric subjects  $\geq 12$  to 17 years old who are  $\geq 45$  kg and willing to swallow the OBV/PTV/RTV and DSV adult formulations. After acceptable pharmacokinetic, efficacy and safety data are available from at least 6 subjects from the  $\geq 12$  to 17 age group who receive the adult regimen, subjects ages  $\geq 9$  to 11 will begin enrollment to be administered the mini-tablet formulations. After acceptable pharmacokinetic, efficacy and safety data are available from at least 6 subjects from the  $\geq 9$  to 11 age group (at least 4 of which have a body weight of 15 to 44 kg) subjects ages  $\geq 3$  to 8 will be enrolled and administered the mini-tablets. In the  $\geq 3$  to 8 year age group, at least 2 subjects each from subgroups  $\geq 3$  to 5 and  $\geq 6$  to 8 years old will be enrolled to ensure that there is adequate information for dosing recommendations for the entire  $\geq 3$  to 8 age group. Up to approximately 12 additional pediatric subjects may be enrolled to

receive the mini-tablet formulation in Part 1 if needed to adequately characterize the pharmacokinetics and determine the final dose strength for a particular age group or subgroup. Subjects will be followed in Part 1 of the study through Post-Treatment Week 24.

In summary, children who are  $\geq 12$  to 17 years old with weight  $\geq 45$  kg and willing to swallow the adult formulations will use the adult formulations of OBV/PTV/RTV with DSV. All other children  $\geq 3$  to 11 years of age will be dosed with the pediatric mini-tablet formulation. For subjects that are not willing to swallow the RBV tablets and are not taking the adult formulations of the DAAs, RBV will be provided as a 40 mg/mL oral solution.

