## **8.2 Determination of Sample Size**

The sample size of 36 subjects in Part 1 will adequately characterize the pharmacokinetics of the AbbVie DAAs to enable dose selection in pediatric subjects.

According to the Prescribing Information of PEGASYS, the SVR24 rate was 47% among 45 treatment-naïve pediatric subjects with HCV GT1 in the NV17424 trial. To show that

the DAA regimen is superior to this current standard of care by 20% in Parts 1 and 2, the lower bound of the 2-sided 95% confidence interval of the SVR12 rate across all subjects in the study must be greater than 67%. For the primary efficacy endpoint of the percentage of subjects with SVR12, if it is assumed 90% subjects would achieve SVR12 then 50 or more subjects would have > 90% power to have a lower bound of 2-sided confidence interval based on normal approximation to the binomial distribution > 67%.

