#### **4.4                   Planned Analysis**

An interim analysis will occur after all subjects in Part 1 or Part 2 have completed the PT Week 12 Visit or prematurely discontinued from study. The database will be versioned after performing appropriate data cleaning. Final data through PT Week 144 will be locked in a later version of the database. SAS® (SAS Institute, Inc., Cary, NC) for the UNIX operating system will be used for all analyses. All statistical tests and all confidence intervals will be two-sided with an  $\alpha$  level of 0.05.

All analyses will be conducted by statisticians and statistical programmers at AbbVie or their designees according to the methodologies specified in this SAP.

There is no intention of changing the study design based on efficacy findings from the PT Week 12 interim analysis. The intention is to follow all subjects who receive study drug for at least 144 weeks following treatment. There will be no statistical adjustment employed due to this interim analysis.

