### **10.3.2 Primary Efficacy Analysis Across Parts 1 and 2.**

The primary efficacy endpoint across Parts 1 and 2 is:

- The percentage of subjects with  $SVR_{12}$  among all subjects.

The  $SVR_{12}$  rate and corresponding 2-sided 95% confidence interval will be presented.

For both the primary and secondary efficacy endpoints, the Wilson's score method will be used to calculate the confidence interval.

According to the Highlights of Prescribing Information of PEGASYS®, the  $SVR_{24}$  rate was 47% among 45 treatment-naïve pediatric subjects with HCV GT1 in the NV17424 trial. To show that the DAA regimen is superior to this current standard of care by 20%, the lower bound of the 2-sided 95% confidence interval of the  $SVR_{12}$  rate across all subjects in the study must be greater than 67%.

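### The protocol and SAP name different confidence intervals for the primary SVR12 success rule, and both power statements use the one the SAP does not apply

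*Protocol*

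**What the plan says.** Protocol 8.1 sets the 95% interval for any simple percentage, naming SVR12, SVR24 and ALT normalization. It is "calculated using normal approximation to the binomial distribution if the percentage is not 0% or 100%; otherwise, Wilson's score method will be used". For its primary and secondary endpoints, the protocol synopsis repeats the rule: "the normal approximation to the binomial distribution will be used if the rate is not 0% or 100%, otherwise the Wilson's score method" applies.

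SAP 10.3.2 states: "For both the primary and secondary efficacy endpoints, the Wilson's score method will be used to calculate the confidence interval". It attaches no condition on the observed rate. SAP 10.5, 10.7 and 10.8 also specify Wilson, so this is a consistent choice within the SAP's analysis sections.

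Protocol 8.2 and SAP 4.3 both assume a true SVR12 of 90% and claim more than 90% power with 50 or more subjects. The power is for the normal-approximation bound: "power to have a lower bound of 2-sided confidence interval based on normal approximation to the binomial distribution > 67" per cent.

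Protocol 8.1 leaves detailed methods to the SAP, and SAP 4.4 says analyses will be conducted "according to the methodologies specified in this SAP".

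**The concern.** The lower limit is the success criterion itself, and under SAP 10.2 it also decides whether SVR24 is tested. A single-arm trial judged against a fixed bound should have one pre-specified way to compute that bound. Here the protocol gives one and the SAP another. The SAP does not mention the departure, and its own power statement is for a rule it does not use.

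The two methods also behave differently. Wald is known to be too liberal for proportions well above one half at this sample size. The protocol's hybrid, with Wald everywhere except 0% and 100%, could give erratic limits near 100%, where SVR12 is expected to fall: Protocol 3.2 cites adult SVR12 "greater than 97% overall in HCV GT1-infected subjects, including those with compensated cirrhosis". At stake are an unambiguous pass mark, control of the one-sided error, and sensible reported intervals.

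**Working it through.** **Inputs.**
- Bound: 67%, that is 47% historical plus 20 points (Protocol 5.6.3 and 8.2).
- Confidence: two-sided 95%, z = 1.95996.
- Planning rate: 90%; power floor of 50 subjects (Protocol 8.2, SAP 4.3).
- Planned enrolment: about 62. Protocol 5.1 adds that "Up to approximately 12 additional pediatric subjects may be enrolled", so I checked every n from 50 to 74.
- My assumptions: 85% as a less favourable true rate, and 97% as the adult level.

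**Formulas**, with p = x/n:
- Wald lower limit: p − z·√[p(1−p)/n]
- Wilson lower limit: {p + z²/(2n) − z·√[p(1−p)/n + z²/(4n²)]} / (1 + z²/n)

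For each rule, the pass mark is the smallest x for which x and all higher counts give a lower limit above 0.67. Error and power are exact binomial tails P(X ≥ pass mark).

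**The plan's own figure.** At n = 50, Wald needs 40 responders (lower limit 68.9%), and P(X ≥ 40 | 0.90) = 99.1%. The stated power of more than 90% is confirmed.

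**The count where the rules disagree at n = 62.** For x = 48, p = 0.7742 and p(1−p)/n = 0.002820.
- Wald: 0.7742 − 1.95996 × 0.05310 = 0.6701. Pass.
- Wilson: z²/(2n) = 0.03098 and z²/(4n²) = 0.00025, so (0.7742 + 0.0310 − 1.95996 × 0.05540)/1.06196 = 0.6559. Fail.
- At x = 49 both pass (68.9% and 67.4%).

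**Pass marks, error and power:**

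| n | Rule | Pass mark | Error at true 67% | Power at 90% | Power at 85% |
|---|---|---|---|---|---|
| 50 | Wald | 40 | 3.17% | 99.1% | 88.0% |
| 50 | Wilson | 41 | 1.44% | 97.5% | 79.1% |
| 62 | Wald | 48 | 5.05% | 99.9% | 96.2% |
| 62 | Wilson | 49 | 2.68% | 99.7% | 92.7% |
| 74 | Wald | 57 | 4.05% | >99.9% | 97.6% |
| 74 | Wilson | 58 | 2.23% | 99.9% | 95.5% |

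**All sizes from 50 to 74.** Wilson needs one more responder at 21 of 25 sizes; the pass marks are equal at 54, 58, 65 and 69. The Wald one-sided error runs from 2.8% to 5.3% (mean 3.9%) and exceeds 2.5% at all 25 sizes. The Wilson error runs from 1.4% to 3.0% (mean 2.2%) and exceeds 2.5% at 8 sizes.

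**Chance of opposite conclusions at n = 62**, P(X = 48): 3.5% at a true 85%, 0.2% at 90%, and about 3 in a billion at 97%.

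**Near 100% at n = 62.** Under the protocol rule, 62/62 has a lower limit of 94.2% (Wilson), but 61/62 has 95.3% (Wald) with an upper limit of 101.5%. One failure therefore gives a higher lower limit than none. Wilson at 61/62 gives 91.4% to 99.7%. The Wald upper limit exceeds 100% at 59, 60 and 61 of 62; the chance of landing there is 12% at a true 90% and 73% at 97%.

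**The case against.** The best reply is that the question is already settled. The protocol defers detailed methods to the SAP, the SAP says its methods will be followed, and it specifies Wilson in four sections. On that reading, the Wald error rates and the limits above 100% describe a rule nobody will apply. The upper limit plays no part in the success criterion. The 85% rate is not a planning value in either document. At the planned 90%, and even more at 97%, the two rules almost never disagree, and the power claim is true under both.

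Most of this stands, and it limits the weight of the point: the trial is not underpowered, and its conclusion is unlikely to change. It does not remove the inconsistency. Protocol 8.1 does more than defer; it names a specific interval for SVR12, and the SAP replaces it without saying so. Deference to the SAP also cannot explain why SAP 4.3 states power for an interval that SAP 10.3.2 does not use.

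It is also fair that editing the protocol is not free, since Protocol 9.1 requires ethics committee approval of amendments.

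**Conclusion.** The concern holds. The current text of the two documents gives different intervals for the primary success rule, and both power statements rest on the one the SAP does not apply. The documents agree only if observed SVR12 is exactly 0% or 100%, and their pass marks coincide at only 4 of the 25 sizes from 50 to 74.

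The difference is at most one responder. It matters for error control if the protocol wording were followed: 5.05% one-sided at 62 subjects against a nominal 2.5%, compared with 2.68% for Wilson. It matters little for the likely result, with about a 0.2% chance of opposite conclusions at 62 subjects and a true 90%.

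These figures assume independent binomial responses with a common rate and a final number dosed between 50 and 74. The 85% and 97% scenarios are my assumptions. This should be fixed because the decision rule needs one definition, not because the sample size is inadequate.

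**What to change.** 1. In the protocol synopsis and 8.1, name Wilson's score as the single interval at all observed rates, matching SAP 10.3.2. Until the protocol is next amended, add a SAP sentence recording that Wilson replaces the protocol's interval.
2. In Protocol 8.2 and SAP 4.3, restate power under Wilson at a true 90%: 97.5% with 50 subjects and 99.7% with 62. The claim of more than 90% remains correct.
3. Give the minimum number of responders as a function of the final number dosed, for example 41 of 50, 49 of 62 and 58 of 74, because enrolment may exceed 62.
4. Note that Wilson is better calibrated than Wald here but not exact (2.68% one-sided at 62).

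The cost is wording only, plus the usual approval step for the protocol text. Sample size is unchanged. Relative to the protocol rule, the pass mark rises by one responder at most sample sizes.

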### **8.1.1 Demographics**

Demographics and baseline characteristics will be summarized by age and weight group separately for each formulation, for all subjects and for all subjects on the adult formulations in the ITT and ITT-3 populations. The baseline value refers to the last non-missing measurement collected before the first dose of study drug is received in Part 1 and on or before Day 1 in Part 2. Demographics include age, birth year, weight, height, body mass index (BMI), height z score (height z score will be calculated using WHO published height-for-age z-score tables), waist circumference, gender, race, ethnicity, geographic region and country. Baseline characteristics will include HCV genotype and sub-genotype (1a, 1b, 1-other and 4 if applicable), IL28B genotype ([CC, CT, or TT] and [CC or non-CC]), IFN treatment history if applicable (treatment-naïve or IFN-based treatment-experienced [prior non-responder {null responder, partial responder, or other unable to specify}, breakthrough, relapse, and interferon experienced-other]), baseline platelets ( $< 90$  or  $\geq 90 \times 10^9/L$ ), baseline albumin ( $< 35$  or  $\geq 35$  g/L), baseline HCV RNA levels (continuous) and ( $< 800,000$  IU/mL or  $\geq 800,000$  IU/mL), baseline fibrosis stage [F0-1, F2, F3, F4]), baseline Fibrotest score, baseline Child-Pugh score (non-cirrhotic, 5, 6, or  $> 6$ ), tobacco use (user, ex-user, or non-user) status, alcohol use (drinker, ex-drinker, or non-drinker) status, and baseline Tanner pubertal staging – genital (males only), breast (females only), and pubic hair development. Summary statistics (N, mean, median, SD, and range) will be generated for continuous variables (e.g., age and height z-score). The number and percentage of subjects will be presented for categorical variables (e.g., gender and race).

## **8.1.2 Efficacy**

Efficacy analyses will be performed across Part 1 and Part 2 using the ITT population.

Plasma HCV RNA levels will be determined for each sample collected by the central laboratory using the COBAS® AmpliPrep/COBAS® TaqMan® HCV Test, v2.0. For this assay, the lower limit of quantification (LLOQ) and the lower limit of detection are 15 IU/mL. HCV RNA results that are detectable but not quantifiable are reported as "HCV RNA is detected, less than 15 IU/mL HCV RNA." HCV RNA results for which no HCV RNA is detected are reported as "HCV RNA not detected."

